For efficacy testing of each test material, each subject is treated on an arm, and has the other arm untreated in order to assess the questing sufficiency of each tick prior to testing it on the untreated arm. The dosimetry study is an examination of dosing behavior for each test material. In that study, each subject will be treated, and will also serve as his or her own untreated control for the dosimeters.

8.2 Experimental Design:

The experiment will be partially randomized by subject. Because the treated condition will be evident to experimenters and subjects, and the test materials are readily distinguishable (opaque lotion versus clear, low-viscosity liquid), neither group will be effectively blinded. The obvious, relatively conservative criteria on which failure is will help to eliminate any influence of experimenter or subject bias.

8.3 Randomization Procedures for Repellent Efficacy Testing:

8.3.1 Allocation of subjects to treatment groups:

Subjects will be assigned to the treatment groups on the basis of a randomly assigned subject number. Subjects will be assigned treatment based on their subject number and the treatment allocation table, which follows.

8.3.2 Treatment allocation table:

Materials will be distributed among subjects as tabulated below. For simplicity, the model shows different set of subjects testing each repellent. However, individual subjects may test more than one repellent, on separate days.

Subject	Lotion	7% Pump	15% Pump
1	X		
2	X		
3	X		
4	X		
5	X		
6	X		
7	X		
8	X		
9	X		
10	X		
11		X	
12		X	
13		X	
14		X	
15		X	
16		X	
17		X	
18		X	
19		X	
20		X	
21			X
22			X

23			X
24			X
25			X
26			X
27			X
28			X
29			X
30			X

8.4. Conditional Boundaries or Limits of Study:

8.4.1. Ambient Host-seeking Pressure:

To be included in the test on a treated limb, each tick must first meet the crossing criterion on the untreated limb, following the procedure for the treated limb (§10.3.6), in the same test period.

8.5. Monitoring of Environmental Conditions During the Study:

Records will be made of environmental conditions (temperature, relative humidity, light intensity) at approximately 1-hour intervals throughout the data collection.

9 STUDY PROCEDURES:

9.1 Test Subjects:

9.1.1 Inclusion criteria, all subjects:

- 9.1.1.1 Age: 18-55 years
- 9.1.1.2 Sex: Male/female
- 9.1.1.3 Race: Any race
- 9.1.1.4 Written consent: (see 9.4, below)
- 9.1.1.5 Language: Speak and read English

9.1.2. Exclusion criteria:

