- 9.1.2.1 Known to be phobic of ticks.

- 9.1.2.2 Known to be sensitive or showing sensitivity to any of the test product ingredients after application.
- 9.1.2.3 Poor physical condition.
- 9.1.2.4 Unwilling to submit to brief query about personal condition.
- 9.1.2.5 Use of insect repellent within 1 day preceding the study.
- 9.1.2.6 Unwilling to refrain from use of perfumed products, alcoholic beverages or smoking after 9 p.m. the evening preceding the test and throughout the test.
- 9.1.2.7 Known to be pregnant or lactating. Pregnancy will be self-checked by each female volunteer on the morning of the repellent test using an OTC test kit provided by Carroll-Loye. Results of each such test will be immediately verified by direct inspection by a technician trained to make that assessment. Only volunteers scored as nonpregnant will be allowed to participate.
- 9.1.2.8 Unable to deliver the test materials or nymphal ticks to own left and right arms.
- 9.1.2.9 Unable to see nymphal ticks on skin or otherwise effectively monitor them on skin.
- 9.1.3.10 Student or employee of the Study Director.

9.1.3 Number of Subjects and Rationale for Sample Sizes:

In both dosimetry and efficacy testing, we will engage 10 subjects per treatment. Each subject is a replicate. It is possible that a single set of 10 individuals could complete all parts of the study. It is much more likely that substantially more than 10 individuals will participate.

The number of subjects is chosen as a compromise between several conflicting factors. In the absence of clear means of estimating the distribution of outcome values, it is difficult to predict an ideal sample size. From a strictly scientific standpoint, an appropriate response under such circumstances would be to increase the sample size, but ethical and economic considerations demand the opposite in

the present study, particularly during the efficacy testing phase.

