Picaridin efficacy (e.g., Carroll¹) indicates that no individual values will be near zero, approximating the exponential model with the normal model is likely justifiable. Using the rule of thumb that a distribution in which the mean is greater than three standard deviations above zero may be regarded as effectively normal, it is sensible to compute and report the normal 95% confidence interval in this study. Alternatively, if tests indicate substantial deviation from a normal distribution, the deviation will be corrected prior to analysis. An exception would be cases in which there is frequent truncation of records ('data censoring') due to subject withdrawals before product failure. In that case, other means of analysis (Kaplan-Meier survival analysis, §11.3.1) will be employed, but that possibility is not strongly related to sample size considerations.

To consider an example, in a study of repellency employing 8 subjects, Cilek et al.² recorded a mean protection time of approximately 180 minutes, with a standard error of about 15 minutes. Had the N been 6, we can roughly predict that the 95% CI would be 148-212. At $N=10$, the estimate would be 155-205. At $N=20$, the interval would be roughly 162-198. Evidently, adding the additional 10 subjects to reach an N of 20 shrinks the interval, in absolute terms, no more than did the addition of 4 subjects to increase the sample size from 6 to 10.

To summarize, in the case of a highly efficacious repellent, adding subjects beyond 6 is likely to increase the precision of the means estimate only slowly. However, the regulatory justification for this study is predicated on an aversion to assuming that efficacy is closely predictable in new formulations. That conservatism is further justified on the basis of the individual and public health importance of

¹ Carroll, S. P. (2006) Evaluation of topical insect repellents and factors that affect their performance. Chapter 12 in *Insect Repellents: Principles, Methods, and Use*, Debboun, M., Strickman, D. and Frances, S. P. (eds.). Boca Raton, Florida, CRC Press.

² Cilek, J. E., Peterson J. L. and Hallmon, C. F. (2004). Comparative efficacy of IR3535 and DEET as repellents against adult *Aedes aegypti* and *Culex quinquefasciatus*. *J. Amer. Mosq. Control Assoc.* 20: 299-304

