prior studies). Because most of the volunteers are researchers and/or have advanced degrees in the life sciences, or work directly with or otherwise regularly encounter biting arthropods in infested habitats, we regard their motivations and decisions to participate as being well-considered and well-informed. Accordingly, we normally accept their decisions to participate if they so choose to following due consideration. Nonetheless, the Study Director retains the final right to refuse participation to any candidate.

9.1.6 Identification method and records retention:

Subjects will initially be identified by first and last name, and assigned a unique number for purposes of this study. Individual data will be entered into the computer for retention and analysis with reference to individual number, not name. Records relating individual names to individual numbers will be retained separately. The Study Director will retain records indefinitely. Subjects may obtain their own records from the Study Director.

9.1.7 Enrollment of alternate subjects and its relation to individual privacy:

We will enroll 3 more subjects than are required to meet our sample size. All subjects will be informed during the consent process that on the day of testing, a small number of subjects may be designated as alternates and sent away after being compensated for coming to the test site. Alternate subjects may return later to replace subjects that initiate testing but withdraw before useful data are generated. They also serve as insurance against any enrolled subjects who fail to appear.

The possibility that any subject may be designated as an alternate will assist in protecting the privacy of any subject that must withdraw in or near the presence of other subjects at the start of the test day (i.e., before treatment and testing begins), for reasons such as a positive pregnancy test result, or for any other personal circumstance.

9.2 Blinding of Study:

None

9.3. Study Material Administration:

Experienced personnel will administer Study Materials to each subject. Test products will be applied volumetrically to the skin surface from a small syringe, and spread on the site as evenly as possible with one fingertip in a surgical glove, using a light rubbing motion. Skin surfaces to be treated are first cleansed with water and a fragrance-free detergent soap, rinsed with a 35% ethanol-in-water solution, then towel-dried.

9.4 Subject Consent:

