We will employ a 15-minute exposure interval as a good minimum in terms of both the temporal resolution of the data set and subject ability to remain focused. Every 15 minutes, each subject selects an unused tick and tests it for active questing behavior as described. To initiate a screening or a repellent challenge, a tick is placed on the ventral arm or proximal palm, in the most hair-free portion, at the first (most distal line). Ticks are manipulated with the bristles of a fine artist's paintbrush. Ticks are placed so that they face the elbow. Ticks may be oriented to locomote toward the margin of the treated area with the gentle action of the paintbrush. Forearms should be held from approximately 30° to vertically above the lab bench surface if that increases the propensity of ticks to travel toward the body.

A crossing is scored if a tick travels at least 3 cm in a vector toward the elbow into the treated area (i.e., at least as far as the third line) within 3 minutes of beginning to move up the arm from the first line. A repulsion is scored when a tick changes its orientation away from, or parallel to, the margin of the treated area upon approach, or does not cross more than 3 cm toward the elbow within 3 minutes of entering the treated area.

Subgroups of approximately three subjects are led by a technician in the monitoring of time, ticks, and tick behavior. Time is monitored by referring to an electric chronometer with a highly visible display. The technician will record any crossings or repulsions as they occur. Repulsions are normally unambiguous reversals of direction. Subjects lift the tick off with the paintbrush after each assessment is complete. Any brushes that come into contact with a test material are discarded. Used ticks are immediately retired from the study by being transferred from the test arm to a container labeled "used".

Scientific Stopping Rule: Subjects are directed to cease tick exposures when a crossing is followed by another crossing within one-half hour, i.e., in either of the subsequent two exposure periods.

10.3.7 Forms for Retention of Source Data:

Dosimetry data will be recorded by a technician on a data form for each test formulation. Repellency data will be recorded by technicians on a repellency data form. Data forms are appended. The recording technicians sign and date the data forms.

10.4 Study Facility:

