Subject effects on dosing behavior will be examined with nonparametric tests for n - sample independent cases (Kruskal-Wallis tests). In multiple regression analysis, the average amount of test material intercepted by each subject's dosimeters, as well as dosing per unit of skin surface area, will be examined in relation to the distance from nozzle to skin, limb size and the number of times the pump was actuated. The relationship between dosing behavior and dosage will also be examined with Spearman-rank correlation tests.

11.3.2. Repellency:

Because all subjects use different ticks, all ticks are used only once, and neither organism interacts directly with conspecifics at the level of the skin and the repellent during data collection, we will analyze data by subject as independent, replicated values. The hypothesis that the test materials will significantly reduce the number of ticks Crossing treated versus untreated skin is *not* the focus of this study. The focus is to compute, for each test material, a reasonable estimate of mean and standard deviation for the duration between application and sufficient repellency breakdown such that two ticks crossing on a subject within a half hour period. That pattern is here assessed at a resolution of 15 minutes.

Complete protection time (CPT) is measured as the length of time from initial application to the First Confirmed Crossing. A FCC is a Crossing followed by another Crossing within 30 minutes. For example, a Crossing at 90 minutes followed by another at 135 minutes is not confirmed, but a third Crossing at 150 minutes would confirm that at 135 minutes, giving a CPT of 135 minutes.

CPT measured in this way will yield a single time value for each subject. Mean CPT will be calculated across all 10 subjects per treatment, and will be presented with standard deviation and 95% confidence interval information as well.

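### Section 9.1.7 lets alternates replace subjects after testing has begun, on an undefined test of usefulness that is not reconciled with the plan to censor withdrawals

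*Protocol*

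**What the plan says.** - **Replacement (§9.1.7).** "We will enroll 3 more subjects than are required to meet our sample size". It is not stated whether the three are per product or overall. On their use after testing has started: "Alternate subjects may return later to replace subjects that initiate testing but withdraw before useful data are generated". The next paragraph of that section deals separately with people who leave before treatment, so replacement after the start is a deliberate provision.
- **Sample size (§9.1.3).** "In both dosimetry and efficacy testing, we will engage 10 subjects per treatment".
- **Blinding (§8.2).** "neither group will be effectively blinded"; §9.2 also states that there is none.
- **Who sees the outcome (§10.3.6).** "The technician will record any crossings or repulsions as they occur". Subjects place and watch the ticks themselves.
- **Withdrawals in the analysis (§9.1.3).** The exception to the normal-theory interval is "frequent truncation of records ('data censoring') due to subject withdrawals before product failure", for which Kaplan-Meier is to be used. §11.3.2 also proposes Kaplan-Meier for CPT in general.
- **Main summary (§11.3.2).** "Mean CPT will be calculated across all 10 subjects per treatment".

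**The concern.** The protocol gives two routes for a treated subject who leaves without a confirmed crossing. One substitutes an alternate; the other keeps the subject as a censored observation. No text says which applies when, who chooses, or whether a replaced subject's record stays in the analysis. Two teams following the protocol could build different analysis sets from the same test day.

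The choice can also be made after the outcome has been partly seen. A subject may show one crossing and withdraw before the next exposures confirm or refute it, and whether that record counts as useful is then judged by people who have watched it. The request for a mean over ten subjects pulls towards substitution, because a censored subject has no observed CPT to average.

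Each subject is a tenth of a product's sample. §9.1.3 itself warns that one unrepresentative subject can bias a small sample and that the absence of replication increases the risk. The results are meant to support labeling (§5.2) and are bridged to other products (§6.1.1).

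**Working it through.** **1. The protocol's own precision figure.** The example in §9.1.3 has mean 180 min and SE about 15 min from 8 subjects.

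- SD = 15 × √8 = 42.4 min.
- At N = 10, SE = 42.4/√10 = 13.4 min, and 180 ± 1.96 × 13.4 gives 153.7 to 206.3. The protocol states 155 to 205.
- With SD 40 (SE 14.1 at n = 8, which fits 'about 15') the interval is 155.2 to 204.8, which matches after rounding.

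The figure reproduces, and nothing in this point changes it.

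**2. Which records the replacement rule can reach.**

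- *Confirmed crossing.* The Scientific Stopping Rule (§10.3.6) ends exposure and the subject has a CPT. This is an observed endpoint, so the rule does not reach it.
- *Leaves before any tick exposure on treated skin.* No outcome has been seen. Replacement is harmless.
- *Exposed, no crossing, then leaves.* Censored under §9.1.3 or replaced under §9.1.7. The protocol does not say which.
- *Exposed, one unconfirmed crossing, then leaves.* The same ambiguity, with an unfavourable record in view.

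The gap is confined to the last two cases.

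**3. A ceiling on the effect.** Assume CPT is Normal(180, 42.4) and that the subjects replaced are exactly the shortest-lasting of ten. The expected shift in the mean is the summed standardised shortfall of those subjects × SD/10:

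- one replaced: 1.54 × 42.4/10 = 6.5 min, or 6.5/13.4 = 0.49 SE;
- two replaced: 2.54 × 42.4/10 = 10.8 min.

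A simulation (200,000 samples, CPT rounded up to the 15-minute grid) gave 6.5, 10.8 and 13.6 min for one, two and three replacements. Coverage of the 1.96-SE interval was 92% with the original ten subjects, and 86%, 78% and 73% after the replacements. When the replaced subjects were chosen without regard to outcome, the mean stayed at 187.5 min (the grid-rounded baseline) and coverage at 92%.

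**4. How reachable that ceiling is.** The expected lowest CPT of ten is 180 − 1.54 × 42.4 = 115 min. With exposures every 15 minutes from about 15 minutes after treatment (§10.2, §10.3.6), such a subject would have completed about seven exposures (15, 30, …, 105 min). The calculation also ranks subjects by realised CPT, and a subject with a realised CPT has already met the endpoint. The rule can hardly produce this pattern in full.

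**5. Does censoring cure it?** Not entirely. In the same model, with one subject of ten censored at 30 minutes regardless of outcome, the Kaplan-Meier median averaged 187.4 min. With the poorest subject censored one exposure before failure it averaged 192.6 min. Censoring keeps the record in the data and visible, but outcome-related withdrawal still biases upward.

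**The case against.** A reader might infer that unblinded staff may drop subjects who perform poorly. The protocol does not support that. The trigger is a withdrawal, which is the subject's free choice (§5.4, §9.1.5.3). Withdrawal by staff during testing is described for skin reaction or illness (§5.4, §9.5), and otherwise exposure ends under the Stopping Rule, which yields a CPT. Staff discretion extends at most to calling an alternate and to the fate of the record left behind.

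A reader might also infer that the protocol has no censoring plan, or that early crossings would be concealed. Neither follows. Kaplan-Meier is named in §9.1.3 and §11.3.2. Technicians sign and date the data forms (§10.3.7), and the final report is audited (§13).

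The two routes can be read together: very early leavers are replaced, later ones censored. A subject censored before the first failure does not change the Kaplan-Meier curve, so replacing such a person loses almost nothing. Details of analysis sets may also sit in a statistical analysis plan that is not at hand.

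Most of this stands, and it narrows the point. It does not remove it. The replacement rule is fixed in the protocol itself, its boundary is a single undefined word, and nothing ties that boundary to a moment before outcomes are seen.

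**Conclusion.** The point holds as a gap in the replacement rule. §9.1.7 permits substitution after testing has begun, on an undefined criterion that can be applied with crossings in view, and it is not reconciled with the censoring route in §9.1.3 or with the ten-subject mean in §11.3.2. The subjects at issue are those exposed after treatment who leave without a confirmed crossing.

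The size of any bias cannot be derived from the protocol, which gives no withdrawal rate and no information on whether withdrawal is linked to performance. It is zero if there is no link. The 6.5 min for one replacement (10.8 and 13.6 for two and three) is a theoretical ceiling. It rests on a normal model taken from the §9.1.3 example and on the poorest performers being exactly those replaced, so it should not be read as an expected effect. The change is worth making because it is cheap and closes a route to selection in a sample of ten.

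**What to change.** - **§9.1.7:** allow replacement only up to a point that precedes any outcome, no later than the first tick exposure on treated skin. Keep every subject exposed after treatment in the analysis: failed if a crossing was confirmed, otherwise censored at the last exposure. Add any alternate tested after a later withdrawal to the sample without removing the subject who left. List all withdrawals and replacements with reasons and crossing records.
- **§11.3.2, with the matching sentence in §9.1.3:** use the Kaplan-Meier estimate whenever any subject is censored, not only when censoring is frequent, since a mean over all ten is then undefined.

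The cost is a few sentences in these sections. A product may occasionally have 11 or more subjects, some of them censored. Subjects' freedom to withdraw is untouched. Censoring will not fully remove bias if withdrawal is itself linked to outcome, which is why the listing of withdrawals is part of the change.

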Before the repellent is applied, subjects will be guided to wash the lower arms with mild, low fragrance soap, rinsing them with a spray of ethyl alcohol (mixed with an equal part of water), and then drying them with a clean towel. A technician will then apply insect repellents to one forearm to give even, complete coverage of the skin on all sides of the arm. The treated area will extend a minimum of 10 cm along the forearm. The amount of repellent to be applied to any limb will be calculated in advance for each subject. The dosing rate will be the product of the subject's limb surface area multiplied by the grand mean (mean of all subject means) rate calculated in the dosimetry data analysis for that test material. Each subject will therefore be dosed at the same rate within a given repellent even if their individual application rates differed from the grand mean.

Three 'orientation' ink dots are arrayed longitudinally on both ventral forearms of each subject, at 3 cm intervals. On the treated arm (or treated portion of the arm if both arms are treated (see §8.3.2) the first dot is 3 cm distal to the treated area, the second dot marks the threshold of the treated area, and the third dot is 3 cm into the treated area. The untreated limb/limb portion has a spatially identical array of 3 lines for tick activity screening. The first dot, used for placement, insures that ticks are not placed within the treated area and so can detect a gradient of repellent density to which to orient. The second dot serves keep subjects aware of where the treated area begins and serves as a reorientation point for re-marking should either the first or the third dot become obscured.

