Spend about 30 minutes practicing handling ticks in the laboratory in preparation for the repellent study. Your trainer will show you how to remove ticks from vials (held in water pans in order to keep ticks from escaping). Your trainer will draw three fine lines with removable ink across your inner forearm, near the wrist, 3 cm apart from one another. From the vial labeled 'Fresh', gently touch the paintbrush tip near the front of a tick's body. It will climb onto the brush. Place the tick on the line nearest your wrist, noting the time as soon as the tick begins to walk toward your elbow. If the tick instead walks toward your hand, elevate your elbow above the hand and use the brush to gently guide the tick back toward the lines. Once it passes the first line, walking toward the elbow, note the time at that point. Observe whether the tick crosses both the second and third lines toward your elbow within three minutes of the start time. After it has crossed the third line, or after three minutes if not, use your brush to remove the tick and place it in the vial labeled 'Used'. If it crossed that line within three minutes, record 'C' on the practice data sheet; otherwise record 'R' for 'repelled'. You will practice these tasks several times in order to familiarize yourself with how to handle the ticks carefully and successfully. You may ask your trainer for advice on how to do this at any time while you are practicing.

1. Study subjects
b. ticks
i. handling
ii. observing movement
(v. 2, 11 June 2007)

Hazardous Material Identification System – (HMIS)

HEALTH – 1

REACTIVITY – 0

FLAMMABILITY – 2

PERSONAL – None

Material Safety Data Sheet

Complies with OSHA's Hazard Communication Standard, 29 CFR 1910.1200

I Trade Name: Cutter Advanced Insect Repellent

Product Type: Insect Repellent Pump Spray

Product Item Number: 53663

Formula Code Number: 21-0827

EPA Registration Number

Manufacturer

Emergency Telephone Numbers

121-89

Chemsico
 Division of United Industries Corporation
 [name]
 [name]

For Chemical Emergency: [name]
For Information: [name]
Prepared by: [name]
Date Prepared: Jan. 4, 2005

II Hazards Ingredient/Identity Information

Chemical	%	OSHA PEL	ACGIH TLV
Picaridin CAS # 119515-38-7	7.00	NE	NE
Ethanol CAS #64-17-5/ 977021-81-0	30.00	1000 ppm	1000 ppm

III Physical and Chemical Characteristics

Appearance & Odor: Water-white with an alcohol odor
Boiling Point: NA

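### In §10.3.6 a tick that turns at the treated edge and then reaches the third line in time is both a repulsion and a crossing; no rule says which prevails, and the training manual scores it only as a crossing

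*Protocol*

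**What the plan says.** Protocol §10.3.6 lays out three marks 3 cm apart. On the treated arm "the first dot is 3 cm distal to the treated area, the second dot marks the threshold of the treated area", and the third lies 3 cm inside, so a crossing covers 6 cm in all. Each challenge is then scored as follows.

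- **Crossing:** "A crossing is scored if a tick travels at least 3 cm in a vector toward the elbow into the treated area", provided it does so "within 3 minutes of beginning to move up the arm from the first line".
- **Repulsion:** the tick either "changes its orientation away from, or parallel to, the margin of the treated area upon approach", or it "does not cross more than 3 cm toward the elbow within 3 minutes of entering the treated area".

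The section gives no order of precedence and no third category. The technician logs each event when it happens, and "Subjects lift the tick off with the paintbrush after each assessment is complete".

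The training manual (§1.b, part D) teaches subjects another rule: "Observe whether the tick crosses both the second and third lines toward your elbow within three minutes of the start time". If it does, the subject writes C; in every other case, R.

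For the endpoint, §11.3.2 states: "A FCC is a Crossing followed by another Crossing within 30 minutes". CPT runs from application to that event. RP, in the same section, is built from challenges without a crossing. §8.2 concedes that the study is not effectively blinded and relies on the plainness of the failure criteria to limit bias.

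**The concern.** CPT is the quantity the study exists to estimate, and §5.2 says the results will be the basis for labeling. Every CPT is assembled from individual crossing calls made by people who know which arm is treated. If two careful observers following the written text can score the same tick differently, the criteria do not give the protection that §8.2 claims for them.

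The mismatch also falls between the people involved. §10.2 has subjects recording crossings, and they are trained on the manual's rule. §10.3.6 has technicians recording crossings and repulsions under its own rule. A tick lifted off early cannot be rescored afterwards, so the matter cannot be repaired at analysis.

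**Working it through.** **Inputs.** From §10.3.6: 3 cm from the first mark to the treated edge, 3 cm from the edge to the third mark, a 3-minute crossing limit from the first mark, and a 3-minute repulsion limit from the edge. From training manual §1.b: one 3-minute window, C or otherwise R. From §11.3.2: the confirmation rule and a worked example.

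**Step 1: apply the rules literally.** Let t1 be the minutes from first mark to edge, t2 the minutes from edge to third mark, and d the distance reached inside the treated area.

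- Crossing: d ≥ 3 cm and t1 + t2 ≤ 3.
- Repulsion: a turn on approach, or not (d > 3 cm with t2 ≤ 3).
- Manual: C if the third line is passed within 3 minutes of the start, otherwise R.

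| Tick | t1 | t2 | Crossing? | Repulsion? | Manual |
|---|---|---|---|---|---|
| Straight, past 3 cm | 1 | 1 | yes | no | C |
| Turns parallel at the edge, then past 3 cm | 1 | 1 | yes (2 ≤ 3) | yes (turn) | C |
| Exactly 3 cm, then stops | 1 | 1 | yes | yes | C, if reaching the line counts as crossing it |
| Straight but slow, past 3 cm | 2 | 2 | no (4 > 3) | no (2 ≤ 3, no turn) | R |
| Enters, gets only 1 cm | 2 | – | no | yes | R |

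So the two §10.3.6 rules overlap (rows 2 and 3) and leave a gap (row 4). For a tick walking steadily without turning, a crossing needs 6 cm / 3 min = 2 cm/min or faster. A repulsion by distance needs 3 cm / 3 min = 1 cm/min or slower. Between those speeds it is neither.

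**Step 2: which of these reach CPT or RP?** Both measures use crossings only.

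- Row 4 is not a crossing under §10.3.6, under the manual, or under a single-clock rule. CPT and RP are unaffected.
- Row 3 satisfies the crossing definition, whose own parenthesis makes the third line the test. It has no effect once that definition is applied.
- Row 2 does reach the endpoint. The text lets an observer score the repulsion at the turn, after which the tick is lifted off and cannot cross. An observer who waits, as the manual teaches, records a crossing.

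**Step 3: direction.** CPT is the earliest crossing that has another within 30 minutes. Deleting a crossing from the record cannot make that time earlier. Calling row 2 at the first turn therefore lengthens CPT or leaves it unchanged.

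**Step 4: size for one subject.** First the protocol's own example, crossings at 90, 135 and 150 minutes: 135 − 90 = 45 > 30, not confirmed; 150 − 135 = 15 ≤ 30, so CPT = 135. This matches §11.3.2. Now suppose one tick that turned and would have crossed is counted:

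- at 105: 105 − 90 = 15 ≤ 30, so CPT = 90;
- at 120: 120 − 90 = 30, which is the second following exposure and still confirms under the stopping rule, so CPT = 90.

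The shift is 135 − 90 = 45 minutes for that subject, or 45 / 10 = 4.5 minutes on the mean of ten.

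**Step 5: scaling, on assumptions only.** No document gives the frequency of such ticks. Suppose the crossing probability rises linearly from 0 at 4 h to 1 at 12 h. Suppose also that, after 2 h, a fixed share of the otherwise non-crossing challenges are ticks that turn and would then cross in time. Mean CPT is about 403 minutes if none of them is counted. If all are counted, it is about 394, 377, 344 and 277 minutes for shares of 2%, 5%, 10% and 20%. This shows how the effect grows with frequency; it is not an estimate of bias in this study.

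**The case against.** The strongest reply is that repulsion is not an analysis variable. CPT and RP depend on crossings, and a crossing has one definition, one clock and one distance. A reader who sees the two clocks might infer that CPT is undefined or biased for slow ticks, or that the rule treats fast and slow ticks unfairly. The documents do not support that. A tick arriving after 3 minutes is a non-crossing under the present text and under any single clock started at the first line. The fast-versus-slow contrast comes from starting the clock there and would remain after the repair. This part of the reply stands in full.

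It also stands that brush orientation is already the same on both arms. §10.3.6 describes it for screening and challenge together, and §8.4.1 has screening follow the treated-limb procedure.

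Two further replies stand only in part. First, §10.3.6 says repulsions are ordinarily clear reversals of direction. But its written rule also counts a merely parallel turn, and the remark itself allows for exceptions. Second, logging events as they happen suggests that the first event ends the challenge. That may be the intention, but the section does not say so, and such a rule would contradict the manual. The manual is not a cure either: it is written for a practice sheet and has the subject note two moments, when the tick starts walking and when it passes the first line, without saying which is the start time.

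**Conclusion.** The point holds for one kind of tick: the one that turns away from or parallel to the edge on approach and would still reach the third line within 3 minutes of leaving the first. §10.3.6 makes it both outcomes with no precedence, and the training manual makes it a crossing. Early scoring can only remove crossings, so any error from that source favours a longer CPT. The second clock and the more-than-3-cm wording are real drafting faults, but have no effect of their own on CPT or RP.

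The size of any bias is unknown because the frequency of such ticks is not given. A single call can move one subject by 45 minutes in the protocol's own example. It should be settled before data collection, because the study is unblinded, leans on plain criteria, and cannot recover a tick already lifted off.

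**What to change.** Put the same rule in §10.3.6, training manual §1.b and the repellency data form:

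- One clock, started when the tick leaves the first line toward the elbow, on both arms.
- Reaching the third line (at least 3 cm into the area) within 3 minutes is a crossing. Every other result at 3 minutes is a repulsion.
- A turn at the margin does not end the challenge before 3 minutes.
- Brush orientation stops once the tick has left the first line, identically on both arms.

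Under this rule every tick in the table falls in exactly one category: rows 1 to 3 are crossings, rows 4 and 5 repulsions.

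The cost is a wording change in three places. Ticks that turn at once must be watched for up to 3 minutes, and some CPTs may come out slightly shorter. Not letting a turn end the challenge is a choice about what counts as repellency. It is the choice the manual already teaches, and it leaves least to the observer's discretion.
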